4.4 Patient Withdrawal and Replacement

If a patient is pregnant, the patient will be withdrawn from study treatment immediately.

A patient may be withdrawn for any treatment related adverse event or clinically significant findings in clinical labs or other vital signs that are deemed by the investigator to pose an unacceptable risk to the patient. If the study is interrupted due to any of the criteria listed above, the patient may undergo unscheduled assessments to evaluate his/her status. Additional subsequent visits may be required to assess event outcomes.

Study treatment may be discontinued, interrupted or dose reduced for any grade 3 adverse event that is possibly or probably related to study treatment. Study treatment will be discontinued for any grade 4 adverse event that is possibly or probably related to study treatment

Patients may also be discontinued from the study at any time for any of the following reasons:

- Adverse event
- Death
- Lost to follow-up
- Investigator decision
- Pregnancy
- Protocol deviation
- Study terminated by Sponsor
- Withdrawal by subject

A patient may be withdrawn from the study at any time due to the following adverse events based on the known safety profile and mechanism of the drug:

- Dehydration requiring hospitalization
- A laboratory result of total cholesterol and triglycerides $> 2 \times$ ULN
- Allergic reaction requiring hospitalization

A patient may be withdrawn from the study at any time due to the following adverse events:

- A laboratory result of ALT or AST $> 3 \times$ ULN, total direct bilirubin $> 2 \times$ ULN or serum creatine > 2.5 ULN
- Abnormal cardiac findings such as a clinically significant abnormal heart rate or rhythm, left bundle branch block with QRS interval > 110 msec or first-degree AV block with PR interval > 220 msec.

A patient may be withdrawn by the investigator or the sponsor if enrollment in the study is deemed inappropriate, the study plan is violated, or for administrative and/or safety reasons.

A patient may elect to discontinue study participation at any time for any reason without prejudice to his/her

future medical care by the physician or at the institution. The investigator will document the specific reason why consent was withdrawn.

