6.3 Serious Adverse Event

An AE should be classified as an SAE if it meets one of the following criteria:

Fatal:	The AE resulted in death.
Life-threatening:	The AE placed the subject at immediate risk of death. This classification does not apply to an AE that hypothetically might cause death if it were more severe.
Hospitalization:	The AE required or prolonged an existing inpatient hospitalization. Hospitalizations for elective medical or surgical procedures or treatments planned before the signing of informed consent in the study or routine check-ups are not SAEs by this definition.
Disabling/ incapacitating:	The AE resulted in a persistent or significant incapacity or substantial disruption of the subject's ability to conduct normal life functions.
Congenital anomaly or birth defect:	An adverse outcome in a child or fetus of a subject exposed to the study treatment before conception or during pregnancy.

Medically significant: The AE did not meet any of the above criteria but could have jeopardized the patient and might have required medical or surgical intervention to prevent one of the outcomes listed above or involves suspected transmission via a medicinal product of an infectious agent.

The Principal Investigator will promptly review all information relevant to the safety of the investigational drug and notify the FDA of any unexpected fatal or life-threatening suspected adverse reaction as soon as possible, but no later than 7 calendar days after receipt of the information. The Principal Investigator will also notify the FDA in an IND safety report of potential serious risks, as soon as possible, but in no case later than 15 calendar days after the Principal Investigator determines that the information qualifies for reporting.

Elective hospitalization and/or surgery for clearly preexisting conditions (i.e., a surgery that has been scheduled prior to the patient's entry into the study) will not be reported as an SAE. All other hospitalizations, including elective hospitalizations for any condition that was not preexisting, will be reported as an SAE.

Any SAE that is ongoing when the patient completes the study or discontinues the study will be followed by the Investigator until the event resolves, stabilizes, or returns to baseline status.

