7.2 Statistical Analysis

Effects of treatment will be compared using Intent-to-Treat principles using ANCOVA with BMI, gender and baseline fasting C4 as covariates. In order to reach 30 subjects, accrual will be set at 36 to replace any volunteer(s) who withdraw prior to taking less than 1 day of dosing. Any Subject who receives more than 1

day of dosing will be consider completed using the Intent-to-Treat analysis.

Primary endpoints are change in fasting serum C4 levels from baseline to Day 28 and change in stool consistency based on Bristol Stool Form Scale, BSFS from baseline to Day 28.

Secondary endpoints are

- Absolute change in stool consistency from baseline to Day 14 and Day 28 of treatment
- Average daily stool consistency score at Day 14 and Day 28 of treatment
- Maximum abdominal pain score rated by patient using an 11-point scale, 0 to 10 inclusive with 0 as none and 10 as worst imaginable pain
- Absolute change in abdominal pain from baseline to Day 14 and Day 28 of treatment
- Number of bowel movements per week
- Change in total fecal bile acid concentration between baseline and Day 28
- Proportion of fecal secretory (CDCA+ DCA) bile acid as measured in a single, random stool sample by a validated laboratory assay.
- Proportion of fecal primary (CDCA + CA) bile acid as measured in a single, random stool sample by a validated laboratory assay.
- Total fecal bile acid concentration in a single, random stool sample as measured by a validated laboratory assay.
- Total aldafermin concentration in serum as measured by a validated laboratory assay

Adverse events (AEs) will be listed and summarized by system organ class and preferred term, as well as according to severity and causality/relationship to study treatment.

Observed values for clinical laboratory tests, vital signs and safety 12-lead ECGs will be summarized by treatment. Observed values will be classified as normal, abnormality that is not clinically significant, and clinically significant abnormality by treatment.

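### Section 4.4 lets adverse events end study participation as well as dosing, so patients kept in the Intent-to-Treat set can lack Day-28 C4 and stool data

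*Combined protocol and SAP*

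**What the plan says.** Section 4.4 describes two different actions.

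- **Stopping study treatment.** This applies to related grade 3 events (where interruption or dose reduction is also allowed), to related grade 4 events, and to pregnancy: "If a patient is pregnant, the patient will be withdrawn from study treatment immediately".
- **Leaving the study.** A general list opens with "Patients may also be discontinued from the study at any time for any of the following reasons" and includes adverse event, investigator decision and, again, pregnancy. A second list begins "A patient may be withdrawn from the study at any time due to the following adverse events based on the known safety profile and mechanism". It covers hospital admission for dehydration or allergic reaction, and a lipid threshold. A third list covers liver, renal and cardiac findings. A closing clause allows removal "if enrollment in the study is deemed inappropriate, the study plan is violated, or for administrative and/or safety reasons".

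One sentence fits neither group clearly: "A patient may be withdrawn for any treatment related adverse event or clinically significant findings in clinical labs or other vital signs". It does not say whether the patient leaves treatment or the study.

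The follow-up described is for safety. Section 4.4 allows unscheduled assessments and says "Additional subsequent visits may be required to assess event outcomes". Section 6.3 says "Any SAE that is ongoing when the patient completes the study or discontinues the study will be followed by the Investigator", and section 6.5 repeats this. None of these provisions collects C4 or stool data.

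Section 7.2 specifies an Intent-to-Treat ANCOVA. The two primary endpoints are change to Day 28 in fasting C4 and in stool consistency. Only volunteers who leave with less than about 1 day of dosing are replaced. Anyone with more than 1 "day of dosing will be consider completed using the Intent-to-Treat analysis". No rule is given for a member of that set without a Day-28 value.

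**The concern.** An Intent-to-Treat comparison at Day 28 needs Day-28 values from patients who stopped the drug. Section 4.4 allows the patients most likely to stop for a drug-related reason to leave before those values are taken, and section 7.2 still counts them. One exit list is tied by the protocol itself to the drug's safety profile and mechanism, so exits could differ between arms.

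A link with the stool endpoint is plausible but unproven. In the constipation study summarised in section 1.3, the 1 mg dose speeded colonic transit at 48 hours (4.29 vs 3.36 on placebo, p = 0.001), although bowel frequency did not differ significantly (p = 0.178). That was a different population. With 15 per arm, each lost patient is 1/15, or about 7%, of an arm.

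**Working it through.** **Step 1: which exits can cost a Day-28 value.**

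| Exit in 4.4 | Action stated | Can it remove the Day-28 value? |
|---|---|---|
| Related grade 3 or 4 event | Treatment only | Not by rule. The diary (6.8) and Visits 4 and 5 (3.5, 3.6) are not barred, but attendance after stopping drug is not stated |
| Treatment-related event or safety finding | Not specified | Only if read as leaving the study |
| Adverse event, or investigator decision on safety grounds | Study | Yes, if before Visit 5 |
| Hospital admission for dehydration or allergy | Study | Yes, if before Visit 5 |
| Lipid, liver, renal or ECG finding | Study | Only at an unscheduled test: the scheduled on-treatment laboratory tests and ECG are at Visit 5 (6.6, 6.7), when Day-28 C4 is drawn |

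The realistic routes are symptomatic adverse events, the two hospitalization triggers and unscheduled findings.

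**Step 2: reproduce the plan's power figures.** Two-sample t-test, two-sided alpha 0.05, noncentral t, differences and SDs from Tables 1 and 2 of section 7.1:

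- Off sequestrant, 9 per group: C4 64.1/45.6 = 1.406 SD, power 79.9%; stool form 1.58/1.12 = 1.411 SD, power 80.2%.
- On sequestrant, 6 per group: C4 90.8/50.6 = 1.794 SD, power 80.0%; stool form 1.08/0.6 = 1.800 SD, power 80.2%.

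The stated 80% reproduces. For 15 per group the synopsis claims about 80% power without giving a difference. Solving the same formula gives d = 1.060 SD.

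**Step 3: illustrate the size.** The documents give no dropout rate after dosing, so k = 1 or 2 affected patients in the active arm of 15 is an assumption. ANCOVA covariates are ignored.

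- *Values missing:* noncentrality = d × √[n₁n₂/(n₁+n₂)]. For 15 vs 14: 1.060 × √(210/29) = 2.85, power 78.5%. For 15 vs 13: 1.060 × √(195/28) = 2.80, power 76.8%.
- *Retained off drug, no residual effect (worst case):* expected difference = 1.060 × (1 − k/15) = 0.989 or 0.918 SD; power at 15 vs 15 is 74.4% or 68.0%. A simulation of 100,000 trials that also carries the extra spread in the active arm gives 73.1% or 65.5%.
- *Retained, half the effect kept:* 1.060 × (1 − k/30); power 77.3% or 74.4%.

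**Step 4: bias.** If the leavers would have shown no effect, a completers-only contrast estimates 1.060 SD where the all-randomised effect is 0.989 or 0.918 SD, an overstatement of 15/14 − 1 = 7% or 15/13 − 1 = 15%. If they resemble those who stay, there is no such bias. The documents do not say which holds.

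**The case against.** **The route is narrow.** Every study-exit trigger is permissive, scheduled laboratory and ECG findings coincide with the Day-28 draw, and the hospitalization triggers are capped because five or more such patients stop the study (section 4.5). This stands and limits the point's reach. It does not remove the general adverse-event exit, and a cap of four is a tolerance, not a forecast.

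**Completed may only mean membership of the Intent-to-Treat set.** That is the natural reading, and it is correct practice. A reader might infer that section 7.2 treats withdrawn patients as having Day-28 data; the text does not say so. The gap is that section 4.4 lets such members leave without the value the analysis needs.

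**The fix lowers power and leaves some gaps.** Both are true. The higher figures for missing values are power for an effect among completers, not for the Intent-to-Treat effect the protocol chose. Patients too ill to fast, consent withdrawals and losses to follow-up would still lack data, and a missing-data rule for section 7.2 is a separate need. The 1.06 SD is also not a stated target. At the Table 1 C4 difference (1.406 SD) and 15 per arm, power is 96.0% with full data, 95.4% or 94.6% with 1 or 2 values missing, and 93.4% or 89.6% with those patients retained at no effect.

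**An off-drug C4 may mostly show washout.** This is a fair estimand argument for a biomarker endpoint, but the protocol has already chosen Intent-to-Treat.

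**Conclusion.** The point holds as a minor, cheap improvement. The stated exit rules work against the stated analysis: section 4.4 permits study exit for adverse events, section 7.2 retains those patients without replacement, and nothing provides for their Day-28 C4 and stool data.

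Two stronger readings might be inferred and are not supported. One is that the protocol requires removal for these events; the wording is permissive, and for the treatment-related sentence it does not say what the patient is withdrawn from. The other is that the primary comparison is biased; no dropout rate is given, and neither the size nor the direction of any bias follows from the documents.

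The power figures rest on an assumed 1 or 2 active patients, an effect of 1.06 SD derived from the 80% claim, and an unadjusted t-test. The power loss from missing values alone is small (80% to 78.5% or 76.8%). The case for change rests on reducing treatment-related missingness.

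**What to change.** In section 4.4, make the adverse-event and safety exits withdrawals from study treatment: the treatment-related sentence, the general adverse-event bullet, both event and finding lists, and investigator or administrative removals made on safety grounds. Pregnancy, now listed under both actions, can be tidied in the same edit.

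Then add a sentence such as: *Unless the patient withdraws consent or the investigator judges a procedure medically unsafe, a patient who stops study treatment keeps the diary and attends Visits 4 and 5 for C4 and stool collection; these data are included in the Intent-to-Treat analysis.* The safety exception is needed because both visits call for a twelve-hour fast.

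The cost is protocol wording and keeping scheduled visits for a few patients off drug; no new visit or assay is needed. The downside is that the Intent-to-Treat effect then includes off-drug time, with the worst-case power shown above.

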3.5 Visit 4 Interim Treatment Testing

About two weeks later, the patient will return after a twelve-hour fast and avoidance of alcohol for 24 hours. The patient will be asked about any changes in eligibility criteria, study medication dosing, concomitant medications and adverse events. Vital signs will be obtained. The patient will turn in any remaining study medication and receive a new supply. The patient will bring in a single, random stool sample and will be given a new stool collection kit to bring in a sample at the next visit. The patient will return the bowel pattern diary and receive a new bowel pattern diary. Blood will be obtained for C4, FGF19 and pk analysis. Urine will be obtained for a pregnancy test for females of child-bearing potential.

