6.6 Clinical Laboratory Tests

Clinical safety laboratory tests will be performed at the study site at Visit 1 Screen or Visit 2 and Visit 5 End of Study. These tests include the Comprehensive Metabolic Panel, calcium, creatinine, sodium, potassium,

albumin, alkaline phosphatase, total bilirubin, carbon dioxide, chloride, glucose, total protein, BUN, AST, and ALT. Hematology includes a CBC with differential. A lipid panel including total cholesterol, HDL, LDL and triglycerides will be performed. Analysis of the urine will be completed by a standard urine dipstick method with microscopy. The investigator will the laboratory report, document the review, and record any clinically relevant changes as AEs.

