6.7 Electrocardiograms

Single 12-lead ECGs will be recorded with subjects in a supine position at Visit 1 Screen and Visit 5 End of Study. Additional ECGs may be taken at any other times, if deemed necessary by the investigator. All ECG tracings will be reviewed by the Principal Investigator or designee.

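### No scheduled test can detect a breach of the section 4.4 laboratory limits while dosing can still be stopped, and four of the section 4.4 decision rules need clearer wording

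*Combined protocol and SAP*

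**What the plan says.** Section 4.4 introduces its laboratory limits with "A patient may be withdrawn from the study at any time due to the following adverse events". The lipid limit, "A laboratory result of total cholesterol and triglycerides" above 2 × ULN, is listed as one of the events chosen "based on the known safety profile and mechanism of the drug". A second list gives ALT or AST above 3 × ULN, a bilirubin limit of 2 × ULN and a creatinine-type limit of 2.5.

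On timing, section 6.6 states: "Clinical safety laboratory tests will be performed at the study site at Visit 1 Screen or Visit 2 and Visit 5 End of Study". The visit descriptions agree. Section 3.3 takes safety bloods at Visit 2 only if they were not taken at Visit 1. Section 3.4 puts the first dose at Visit 3. At Visit 4 the patient attends fasting and section 3.5 says "Blood will be obtained for C4, FGF19 and pk analysis"; urine is taken for a pregnancy test where relevant and a new drug supply is given out. Section 3.6 takes the full safety panel at Visit 5, when unused drug is returned.

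Section 6.6 asks the investigator to "record any clinically relevant changes as AEs", and section 3.6 repeats a clinically significantly changed test in 30 days' time. For ECGs, section 6.7 says "Single 12-lead ECGs will be recorded with subjects in a supine position at Visit 1 Screen and Visit 5 End of Study" and allows extra tracings if the investigator thinks them necessary.

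**The concern.** A withdrawal limit protects a patient only if a result arrives while there is still treatment to stop. The protocol itself ties the lipid limit to what is known about the drug, yet schedules no lipid result between first dose and the end of treatment. The same holds for transaminases, bilirubin and creatinine. Pregnancy, which is also a ground for withdrawal, is re-tested at Visit 4; the laboratory limits are not.

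What is at stake is avoidable exposure in a patient with a silent rise: up to about two further weeks of daily dosing after a point at which fasting blood was drawn anyway. A second, smaller problem is that several of the rules cannot be applied exactly as written, so two investigators could act differently on the same result.

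**Working it through.** The plan gives no figure to reproduce. The check sets the limits against the schedule.

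| 4.4 limit | On the panel listed in 6.1 and 6.6? | Before first dose | Visit 4 | Visit 5 |
|---|---|---|---|---|
| Total cholesterol and triglycerides, 2 × ULN | Both listed | Yes | No | Yes |
| ALT or AST, 3 × ULN | Both listed | Yes | No | Yes |
| Bilirubin, 2 × ULN | Total only; the limit names a direct fraction | Yes (total) | No | Yes (total) |
| Creatinine, 2.5 (unit unclear) | Listed | Yes | No | Yes |

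**Intervals**
- Inputs: 28-day treatment period (abstract), Visit 4 about two weeks after Visit 3 (3.5), screening within 28 days before first dose (6.1).
- Scheduled measurements of any of the four limits after first dose and before Visit 5: 0.
- Longest possible gap between consecutive safety panels: 28 + 28 = about 56 days.
- With a Visit 4 panel, the longest dosed stretch without a scheduled safety laboratory falls from about 28 to about 14 days.
- Dosing days left to act on a Visit 4 result: 28 − 14 = 14, less the review time. Assuming review in 3 working days (3 to 5 calendar days), 14 − 3 = 11 or 14 − 5 = 9 days remain.

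**Wording of the rules**
- *Lipids.* Joining the two lipids with *and* means, read literally, that both must exceed 2 × ULN. Whether either alone was meant is not stated.
- *Bilirubin.* Sections 4.4 and 4.3 (exclusion 12) both call it total and direct at once. The listed panel reports total bilirubin only.
- *Creatinine.* Section 4.4 names creatine, with 2.5 ULN as the limit; exclusion 13 uses creatinine above 2.5 mg/dL. The two limits coincide only if the ULN is 1.0 mg/dL. The documents give no ULN. Assuming 0.9 to 1.3 mg/dL, 2.5 × ULN runs from 2.5 × 0.9 = 2.25 to 2.5 × 1.3 = 3.25 mg/dL.
- *Causality.* The mandatory grade 4 stop and the permissive grade 3 rule name events *possibly* or *probably* related. Section 6.5 has a further, stronger category, *Related*, which neither rule names.

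**The case against.** The best defence is that nothing is contradicted. The limits say a patient may be withdrawn; *at any time* gives permission to act and does not promise a test. Treatment is short, Visit 4 already covers adverse events, concomitant medication and vital signs, and the investigator can discontinue a patient on judgement. The liver and lipid data at 1 mg that would show whether a Day 14 panel is needed may sit in the investigator's brochure, which is not part of these documents. All of this is fair, and it limits the force of the point. It does not close the gap: discretion needs a result to act on, and a symptomless rise would not prompt an unscheduled test. Section 4.4 mentions unscheduled assessments only once a criterion has interrupted the study for that patient.

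On causality, section 6.5 defines *Related* partly by the event abating when drug is stopped, so an ongoing grade 4 event would usually still be classed as possibly or probably related. Section 4.4 also separately permits withdrawal for any treatment-related event. This narrows the gap, but an event that abates on interruption can earn the label before permanent discontinuation is decided.

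On creatinine, a withdrawal limit need not equal an exclusion limit. That is right; the fault is the wrong analyte name and the unclear unit, not the difference itself.

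A reader might go further and infer that the QRS and PR values in 4.4 are also unmonitored numeric limits. They are not free-standing: the text reads "left bundle branch block with QRS interval > 110 msec", and the PR value is likewise attached to first-degree AV block. Both are examples of abnormal cardiac findings, and section 6.7 allows extra ECGs.

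**Conclusion.** The point holds as a safety-monitoring gap that should be corrected. Four permissive laboratory limits have no scheduled measurement between first dose and Visit 5, and four sets of rules (lipids, bilirubin, creatinine, grade 3/4 causality) need tidying. This rests on the text of 3.3 to 3.6, 4.4 and 6.6, which agree with one another; only the 9 to 11 days and the creatinine range depend on assumed inputs.

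A reader might infer that a known share of patients will pass a limit unseen, or that the trial's conclusions are at risk. The documents support neither. They give no rate of such rises at 1 mg, so no expected count can be stated. The gap does not touch the primary endpoints, power or type I error.

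**What to change.** **Schedule.** In 3.5 and 6.6, add the existing chemistry and lipid panel to the fasting Visit 4 draw. State that results are reviewed promptly against the 4.4 limits and the patient's own baseline. The baseline matters because 4.3 sets no lipid limit for entry, so a high Visit 4 value may predate treatment. Whether to add a Visit 4 ECG is a question for the clinicians.

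**Blind.** If lipid values are withheld from blinded staff, let the laboratory's out-of-range flag or the independent monitor of 8.3 release only values past the limit. Pharmacy staff who hold assignments cannot do this, because 5.5 keeps them out of all other study activity.

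**Follow-up.** Ask any patient whose drug is stopped to keep the diary and attend Visit 5, so that Day 28 C4 and stool consistency are still collected.

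**Wording**
- Grade 3 and grade 4 rules: possibly related, probably related or related.
- Creatinine: correct the analyte and state the intended unit, mg/dL or × ULN.
- Lipids: state whether both or either must exceed 2 × ULN.
- Bilirubin, in 4.4 and exclusion 12: state total, or add direct bilirubin to the panel.

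**Cost.** About 30 panels, or 36 at full accrual, with no extra visit or fast; an IRB-approved amendment; a small risk that lipid values hint at assignment; and possibly a few mid-treatment stops in either arm.

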4.2 Inclusion Criteria

Patients must meet ALL of the following inclusion criteria to be eligible for enrollment into the study:

1. Aged 18 to 75 years, inclusive at Visit 1 Screen.
2. Clinical diagnosis of functional diarrhea or IBS with diarrhea according to Rome III or IV criteria at Visit 1 Screen.
3. Clinical laboratory evidence of BAM (20-22), with at least one of the following results recorded in their past medical history:
 - Serum C4 \geq 52 ng/mL
 - Fecal BA $>$ 2337 μ moles / 48 hours
 - Total fecal BA $>$ 1000 μ moles / 48 hours + 4 % primary BA
 - Fecal primary BA $>$ 10% / 48 hours
4. Body mass index (BMI) 18.0 to 45.0 kg/m², inclusive at Visit 1 Screen
5. Understands the study procedures, is willing and able to comply with the study procedures, and is able to give informed consent
6. If treated with any of the following medications, dosing must be stable for 30 days prior to Visit 1 Screen. Patient must agree to maintain the same dose of medication throughout the study:
 - Tricyclic antidepressants, selective serotonin reuptake inhibitors (SSRIs) and serotonin and norepinephrine reuptake inhibitors (SNRIs).
 - Bile Acid sequestrants such as colestipol, cholestyramine and colestevam.
7. Patients must use one highly effective method of contraception for 30 days before the study through 90 days after study completion for males and through 30 days after study completion for females. Highly effective methods of contraception include
 - Oral, implantable, subdermal or injectable hormonal contraceptives
 - Standard intrauterine device or vaginal ring
 - Male or female condoms and diaphragms used with spermicide
 - Abstinence from heterosexual intercourse
 - Female partners exclusively sexually active with a surgically sterilized male partner
 - Females who are surgically sterile prior hysterectomy, bilateral salpingectomy, or bilateral oophorectomy) or postmenopausal (defined as: 12 consecutive months with no menses) are not considered to be of childbearing potential

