4.3 Exclusion Criteria

Patients who meet ANY of the following exclusion criteria will not be eligible for enrollment into the study:

1. Pregnant or lactating
2. Structural or metabolic diseases/conditions that affect the gastrointestinal system
3. Use of the following medications at least 14 days prior to Visit 1 throughout the duration of the treatment period:
 - Patients may elect to withdraw from bile acid sequestrants such as colestipol, cholestyramine and colestevam or they may continue but they must continue at the same dose throughout the study.
 - GI medications including:
 - Anti-nausea agents including trimethobenzamide, promethazine, prochlorperazine, dimenhydrinate, hydroxyzine
 - Osmotic laxative agents including lactulose, sorbitol or PEG solutions as Miralax and Glycolax
 - Prokinetic agents including tegaserod, metoclopramide, prucalopride, domperidone, erythromycin, clarithromycin and azithromycin.
 - 5-HT3 antagonists including alosetron, ondansetron, tropisetron.
 - Patients may use Gabapentin if they are on a stable dose, which is not greater than 1200 mg a day.
 - Drugs with a known pharmacological activity at 5-HT4, 5-HT2b or 5-HT3 receptors including tegaserod, ondansetron, granisetron and tropisetron
 - All narcotics including codeine, morphine, and propoxyphene, either alone or in combination
 - Anti-cholinergics including dicyclomine, hyoscyamine, propantheline.
 - Antimuscarinics
 - Tramadol
 - Peppermint oil
 - Systemic antibiotics and antibiotics directed at colonic flora including rifaximin and metronidazole
5. Clinically relevant changes in dietary, lifestyle, or exercise regimen within 30 days prior to Visit 1 Screen and throughout the duration of the study
6. Any colonic or major abdominal surgery including bariatric surgery, gastric banding, stomach

surgery and intestinal or colonic surgery. Procedures such as appendectomy, cholecystectomy, hysterectomy, caesarean section, or polypectomy are allowed as long as they have occurred at least 3 months prior to Visit 1 Screen.

7. History of colorectal cancer, inflammatory bowel disease, diverticulitis, ischemic colitis, microscopic colitis or celiac disease
8. History of organic abnormalities of the GI tract, intestinal obstruction, stricture, toxic megacolon, GI perforation, or impaired intestinal circulation.
9. Other GI diseases such as GI bleeding or ulcerations

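### Section 4.4 allows a randomised patient to be taken out of the study, not only off study drug, for a protocol deviation; if used at or before Visit 4, both Day 28 primary endpoint values are lost and not replaced.

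*Combined protocol and SAP*

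**What the plan says.** **Leaving the study.** Section 4.4 introduces a list with "Patients may also be discontinued from the study at any time for any of the following reasons". Protocol deviation and investigator decision are both on it. A later sentence reads "A patient may be withdrawn by the investigator or the sponsor if enrollment in the study is deemed inappropriate, the study plan is violated", and goes on to administrative and safety reasons.

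**Stopping drug only.** The same section has a separate action for adverse events: "Study treatment may be discontinued, interrupted or dose reduced for any grade 3 adverse event". Grade 4 events and pregnancy are also worded as stopping study treatment.

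**Rules that continue after randomisation.** Inclusion 6 (4.2), for antidepressants and bile acid sequestrants: "Patient must agree to maintain the same dose of medication throughout the study". Exclusion 3 (4.3): "Use of the following medications at least 14 days prior to Visit 1 throughout the duration of the treatment period", and, for sequestrants, "they may continue but they must continue at the same dose throughout the study". Exclusion 5: "Clinically relevant changes in dietary, lifestyle, or exercise regimen within 30 days prior to Visit 1 Screen and throughout the duration of the study".

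**When a breach would surface.** At Visit 4, about two weeks into treatment: "The patient will be asked about any changes in eligibility criteria, study medication dosing, concomitant medications and adverse events". Visit 5 (3.6) asks the same.

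**Endpoints and analysis.** Sections 2.2 and 7.2 define both primary endpoints, fasting C4 and BSFS stool consistency, as change from baseline to Day 28. Visit 5 is the only visit that takes the Day 28 C4 and the second on-treatment diary. Section 7.2 specifies ANCOVA on Intent-to-Treat principles. It uses accrual of 36 to reach 30 by replacing those who withdraw around the first day of dosing, and counts anyone dosed for more than 1 day as completed.

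**The concern.** Under Intent-to-Treat, a patient who breaks a conduct rule remains in the randomised comparison, and the outcome is still measured if possible. Section 4.4 allows the opposite: a patient willing to attend Visit 5 can be taken out of the study because of a deviation. Such a patient leaves at most a Day 14 C4 and the first on-treatment diary. Being counted as completed does not create a Day 28 value, so ANCOVA on the change to Day 28 has nothing to use for either primary endpoint.

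The trial plans 15 patients per arm. At that size an avoidable loss is worth preventing, particularly when the visit that would prevent it is already scheduled.

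**Working it through.** **1. Tracing the loss.**
- The first dose is taken at Visit 3 (3.4), so almost any deviation found during treatment up to Visit 4 falls beyond the first-day replacement rule in 7.2.
- Section 4.4 describes no early-termination endpoint visit. Its unscheduled assessments are optional and follow the safety criteria.
- Section 7.2 names no imputation, mixed model or other missing-data method.
- A deviation after Visit 4 would ordinarily come to light at Visit 5, when the Day 28 data are taken anyway. The path to loss is therefore a deviation found at or before Visit 4 and followed by removal.

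**2. Reproducing the plan's figures.** Section 7.1 gives differences detectable with 80% power at two-sided 0.05. The two-sample t-test has power P(|T| > t(0.975, df)), where T is noncentral t with df = n1 + n2 − 2 and noncentrality d/√(1/n1 + 1/n2).

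| Stratum | Detectable d (SD) | C4, ng/mL | BSFS, points |
|---|---|---|---|
| Off sequestrant, 9 per group | 1.407 | 1.407 × 45.6 = 64.2 (stated 64.1) | 1.407 × 1.12 = 1.58 (stated 1.58) |
| On sequestrant, 6 per group | 1.796 | 1.796 × 50.6 = 90.9 (stated 90.8) | 1.796 × 0.6 = 1.08 (stated 1.08) |

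All four agree to rounding.

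**3. Cost of a lost Day 28 value.** At 15 v 15, 80% power requires d = 1.060, with noncentrality 1.060/√(2/15) = 2.90 on 28 df. With one patient lost it is 1.060/√(1/15 + 1/14) = 2.85 on 27 df.

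For the scale in clinical units, pool the table SDs over the planned 18 patients off and 12 on sequestrant:
- BSFS: √((18 × 1.12² + 12 × 0.6²)/30) = 0.947
- C4: √((18 × 45.6² + 12 × 50.6²)/30) = 47.66

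| Patients with Day 28 data | Power at d = 1.060 | Detectable d at 80% | BSFS, points | C4, ng/mL |
|---|---|---|---|---|
| 15 v 15 | 80.0% | 1.060 | 1.00 | 50.5 |
| 15 v 14 | 78.5% | 1.080 | 1.02 | 51.5 |
| 14 v 14 | 77.0% | 1.100 | 1.04 | 52.4 |
| 13 v 13 | 73.7% | 1.145 | 1.08 | 54.6 |
| 12 v 12 | 69.9% | 1.197 | 1.13 | 57.0 |

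Per patient lost: (80.0 − 78.5)/1 = 1.5 points for the first, and (80.0 − 69.9)/6 = 1.7 on average over six. The number lost is assumed, because the documents give none. Any dropout of the same size costs the same.

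**4. Cost of keeping the patient.** A retained Day 28 value carries the effect of the deviation. As an illustration, take a sequestrant change. Mean C4 in Tables 1 and 2 is 72.3 off and 112.5 on sequestrant, a gap of 40.2 ng/mL. If one of 15 patients shifts by the whole gap, the arm mean moves by 40.2/15 = 2.68 ng/mL.
- Against the treatment effect: d = (50.51 − 2.68)/47.66 = 1.004, power 75.6%.
- With the treatment effect: d = (50.51 + 2.68)/47.66 = 1.116, power 83.9%.
- A quarter of the gap against the effect (40.2 × 0.25/15 = 0.67): power 78.9%.

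The comparison is 78.5% if the patient is lost.

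**The case against.** **Removal is optional.** Every withdrawal clause is permissive, and 8.7 asks for a case-by-case view of what a deviation means for participation and for the safety or efficacy assessment. This stands. A reader might infer that a breach of an eligibility rule during treatment must lead to removal. No sentence says so, and even treating such a breach as a deviation is an inference. What remains is that nothing tells the investigator to keep the patient to Visit 5.

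**The wording is not clean.** The study-plan sentence does not say what the patient is withdrawn from. Pregnancy appears both as a reason to stop treatment and as a reason to leave the study, and the list also includes death and loss to follow-up, so it reads partly as disposition codes. This stands too. The point rests on the list, which expressly concerns discontinuation from the study and includes protocol deviation.

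**The larger gap is in 7.2,** which has no rule for a missing Day 28 value from any cause. True, but a missing-data rule does not recover a measurement that could have been taken.

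**Data after a deviation are contaminated.** For C4 after a sequestrant change the effect need not be slight. Under the full-shift assumption, keeping the patient costs more power (75.6%) than losing the patient (78.5%). This stands as a real downside. The case for retention is that it matches the Intent-to-Treat analysis the plan has chosen; a power gain is not guaranteed.

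**Bias.** A reader might infer that removals would follow poor response. The documents do not support this: loperamide rescue is allowed within limits (5.7), study staff are blinded, and no removal rate is given by arm or overall.

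**Conclusion.** The concern holds in a limited form. Section 4.4 permits removal from the study for a deviation. If this is done at or before Visit 4, it produces an avoidable missing value on both primary endpoints, which 7.2 neither replaces (once the patient has been dosed for more than 1 day) nor fills. That works against the stated Intent-to-Treat analysis. It does not formally contradict it, since removal is not mandatory and 7.2 still counts the patient.

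The size is about 1.5 points of power per patient lost, from the stated level of about 80% at 15 v 15. This assumes a two-sample t-test and the SDs of Tables 1 and 2 used as the protocol uses them, which are not SDs of change. Removing 3 df for the ANCOVA covariates barely changes the power figures (78.5%, 77.0%, 73.5% and 69.6% for the four reduced sample sizes). How many patients would be affected, and whether the result would be biased, cannot be derived. The change is worth making because it is cheap.

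**What to change.** **In 4.4, add:** a protocol deviation, prohibited-drug use, a change in a stable-dose drug, or ineligibility found after randomisation may lead to stopping study drug, but is not by itself a reason to leave the study. This also applies when the ground given is investigator decision or administrative reasons; otherwise the same removal could be made under another label. Unless the patient withdraws consent or safety prevents it, the patient is asked to attend Visit 5 for C4 and the diary and is analysed as randomised.

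**In 7.2, add** a sensitivity analysis that excludes Day 28 values obtained after a major deviation, with major deviation defined before unblinding.

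**Leave alone:** the eligibility question at Visits 4 and 5, which is a general prompt for newly emerging safety exclusions; sections 4.2 and 4.3; safety withdrawal; and the patient's right to leave.

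**Cost:** a few sentences and one extra analysis, with no new visit or sample. Section 5.6 already records all medication. The downside is that retained values include the effect of the deviation. For a sequestrant change, that effect on C4 may not be small and can go in either direction, which the sensitivity analysis is there to show. The change does not supply a rule for Day 28 values missing for other reasons.
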